#### 18.6.3.1. C-SSRS Variables & Derivations

The following outcomes are C-SSRS categories have binary responses (yes/no). The categories have been re-ordered from the actual scale to facilitate the definitions of the C-SSRS endpoints, and to provide clarity in the presentation of the results.

C-SSRS consists of the following categories:

- Category 1 – Wish to be Dead
- Category 2 – Non-specific Active Suicidal Thoughts
- Category 3 – Active Suicidal Ideation with Any Methods (Not Plan) without Intent to Act
- Category 4 – Active Suicidal Ideation with Some Intent to Act, without Specific Plan
- Category 5 – Active Suicidal Ideation with Specific Plan and Intent
- Category 6 – Preparatory Acts or Behavior
- Category 7 – Aborted Attempt
- Category 8 – Interrupted Attempt
- Category 9 – Actual Attempt (non-fatal)
- Category 10 – Completed Suicide

The categories of the C-SSRS are not mutually exclusive. Subjects will be counted in each category for which they have an event.

#### C-SSRS Composite Endpoints

- The following composite endpoints for the C-SSRS will be derived as follows.
- Suicidal Ideation: A “yes” answer at any time during treatment to any one of the five suicidal ideation questions (categories 1-5) on the C-SSRS.

---

Document:

Author:

Version Number:  
Version Date:

Final Draft  
11APR2019

Template No: CS\_TP\_BS016 Revision 4  
Effective Date: 01Apr2016

Reference: CS\_WI\_BS005

- Suicidal Behavior: A “yes” answer at any time during treatment to any one of the five suicidal behavior questions (categories 6-10) on the C-SSRS.
- Suicidal Ideation or Suicidal Behavior: A “yes” answer at any time during treatment to any one of the ten-suicidal ideation and behavior questions (categories 1-10) on the C-SSRS.
- Self-injurious behavior without suicidal intent is also a C-SSRS outcome (although not suicide-related) and has a binary response.

#### 18.6.3.2. Analyses of C-SSRS Variables

The number and percentage of subjects with an event in each of the 10 categories, composite endpoint, or with non-suicidal self-injurious behavior at screening visit will be presented using Screening/Baseline version for the “Lifetime” questionnaire and the “Past 1 Month” questionnaire. For all subsequent visits where C-SSRS is administered “Since Last Visit” version will be used. The percentage will be presented by treatment.

Safety population will be used for all C-SSRS summaries and listings.

The following comparative endpoints will also be presented (n/m %), where “Treatment emergence” is used for outcomes that include events that first emerge or worsen and “Emergence” is used for outcomes that include events that first emerge.

- Treatment-emergent suicidal ideation compared to recent history: An increase in the maximum suicidal ideation score during treatment from the maximum suicidal ideation category at Baseline (C-SSRS scales taken during the specified pre-treatment period; excludes “lifetime” scores from the Baseline C-SSRS scale or Baseline/Screening C-SSRS scale).
- Treatment-emergent serious suicidal ideation compared to recent history: An increase in the maximum suicidal ideation score to 4 or 5 on the C-SSRS during treatment from not having serious suicidal ideation (scores of 0-3) at Baseline (C-SSRS scales taken during the specified pretreatment period; excludes “lifetime” scores from the Baseline C-SSRS scale or Baseline/Screening C-SSRS scale).
- Emergence of serious suicidal ideation compared to recent history: An increase in the maximum suicidal ideation score to 4 or 5 on the C-SSRS during treatment from no suicidal ideation (scores of 0) at Baseline (CSSRS scales taken during the specified pre-treatment period; excludes “lifetime” scores from the Baseline C-SSRS scale or Baseline/Screening C-SSRS scale).

---

Document:

Author:

Version Number:  
Version Date:

Final Draft  
11APR2019

Template No: CS\_TP\_BS016 Revision 4  
Effective Date: 01Apr2016

Reference: CS\_WI\_BS005

- Improvement in suicidal ideation at a time point of interest compared to Baseline: An improvement in this endpoint can be considered as a decrease in suicidal ideation score at the time point of interest (e.g., the last measurement during treatment) from the baseline measurement (e.g., the measurement taken just prior to treatment). This analysis should only be performed for studies in which a baseline C-SSRS can be defined (i.e., having improvement from the worse event over a lifetime is not clinically meaningful).
- Emergence of suicidal behavior compared to all prior history: The occurrence of suicidal behavior (categories 6-10) during treatment from not having suicidal behavior (categories 6-10) prior to treatment (includes “lifetime” and/or “screening” scores from the Baseline C-SSRS scale, Screening C-SSRS scale, or Baseline/Screening C-SSRS scale, and any “Since Last Visit” from the Since Last Visit C-SSRS scales taken prior to treatment).

Note that missing data should not be imputed.

The following summaries will be provided for the C-SSRS data:

- The number and percentage of subjects with each type of suicidal ideation and suicidal behavior will be summarized by treatment
- The number and percentage of subjects with treatment emergent suicidal ideation, serious suicidal ideation, and suicidal behavior will be summarized by treatment
- Responses to each of the questions on the C-SSRS will be listed

## 19. DATA NOT SUMMARIZED OR PRESENTED

The other variables and/or domains not summarized or presented are:

- Comments
- These domains and/or variables will not be summarized or presented, but will be available in the clinical study database, SDTM and/or ADaM datasets.

---

Document:

Author:

Version Number:  
Version Date:

Final Draft  
11APR2019

Template No: CS\_TP\_BS016 Revision 4  
Effective Date: 01Apr2016

Reference: CS\_WI\_BS005

## APPENDIX 1. PROGRAMMING CONVENTIONS FOR OUTPUTS

### DATES & TIMES

Depending on data available, dates and times will take the form yyyy-mm-ddThh:mm:ss.

### PRESENTATION OF TREATMENT GROUPS

For outputs, treatment groups will be represented as follows and in that order:

Treatment Group	For Tables, Listings and Graphs
Oral Lurasidone 80mg	Oral Lurasidone 80mg
Inj. Lurasidone 30mg	Inj. Lurasidone 30mg
Inj. Lurasidone 75mg	Inj. Lurasidone 75mg
Inj. Lurasidone 150mg	Inj. Lurasidone 150mg
Inj. Lurasidone 300mg	Inj. Lurasidone 300mg
Inj. Lurasidone 450mg	Inj. Lurasidone 450mg
Inj. Placebo	Inj. Placebo

---

Document:

Author:

Version Number:  
Version Date:

Final Draft  
11APR2019

Template No: CS\_TP\_BS016 Revision 4  
Effective Date: 01Apr2016

Reference: CS\_WI\_BS005

## APPENDIX 2. PARTIAL DATE CONVENTIONS

Imputed dates will NOT be presented in the listings.

### ALGORITHM FOR ADVERSE EVENTS:

#### ORAL LURASIDONE TABLET PERIOD

START DATE	STOP DATE	ACTION
Known	Known	If start date < oral tablet start date, then not AE If start date >= oral tablet start date and before injection start date, then AE
	Partial	If start date < oral tablet start date, then not AE If start date >= oral tablet start date, and before injection start date then AE
	Missing	If start date < oral tablet start date, then not AE If start date >= oral tablet start date and before injection start date, then AE
Partial, but known components show that it cannot be on or after oral tablet start date	Known	Pre-treatment events
	Partial	Pre-treatment events
	Missing	Pre-treatment events
Partial, could be on or after oral tablet start date and before injection start date,	Known	If stop date < oral tablet start date, then Pre-treatment events If stop date >= oral tablet start date and before injection start date, then AE
	Partial	Impute stop date as latest possible date (i.e. last day of month if day unknown or 31st December if day and month are unknown), then: If stop date < oral tablet start date, then Pre-treatment events If stop date >= oral tablet start date and before injection start date, then AE
	Missing	Assumed AE

Document:

Author:

Version Number:  
 Version Date:

Final Draft  
 11APR2019

Template No: CS\_TP\_BS016 Revision 4  
 Effective Date: 01Apr2016

Reference: CS\_WI\_BS005

START DATE	STOP DATE	ACTION
Missing	Known	If stop date < oral tablet start date, then Pre-treatment events If stop date >= oral tablet start date and before injection start date, then AE
	Partial	Impute stop date as latest possible date (i.e. last day of month if day unknown or 31st December if day and month are unknown), then: If stop date < oral tablet start date and before injection start date, then not AE If stop date >= oral tablet start date and before injection start date, then AE
	Missing	Assumed AE

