## 4.4. DETERMINATION OF SAMPLE SIZE

There will be no formal estimation for the sample size as no previous human PK data are available for lurasidone injectable suspension and the primary endpoints are safety. The sample size of 8 subjects per cohort (6 lurasidone injectable suspension subjects and 2 placebo subjects) is selected based on clinical and practical considerations for a study of this design.

Approximately 70 subjects are planned overall to ensure that up to 40 subjects receive lurasidone injectable suspension or placebo.

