## 6.1. SAFETY [SAF] POPULATIONS

### 6.1.1. ORAL LURASIDONE SAFETY [OSAF] POPULATION

The Oral Lurasidone safety population (OSAF) will contain all subjects who signed the study specific informed consent and received at least one dose of Lurasidone oral tablet.

This population will be used for analysis of concomitant medications and adverse events data along with ISAF population.

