#### **18.1. PRETREATMENT EVENTS AND ADVERSE EVENTS**

Pretreatment events will be recorded from the time informed consent is provided at screening until the Document:

Author:

Version Number:  
Version Date:

Final Draft  
11APR2019

Template No: CS\_TP\_BS016 Revision 4  
Effective Date: 01Apr2016

Reference: CS\_WI\_BS005

time of first lurasidone oral tablet dose administration at Day-7.

Adverse events will be collected for each subject from immediately after the first lurasidone oral tablet dose administration at Day -7 until the follow-up visit at Day 61 ( $\pm 2$ ). Adverse Events (AEs) will be coded using Medical Dictionary for Regulatory Activities (MedDRA) central coding dictionary, Version 21.0 or higher.

- Adverse Events for the Oral Lurasidone tablet period is defined as an AE that started on or after the first dose of the oral lurasidone tablet.
- Adverse Events for the double-blind Injection period is defined as an AE that started on or after the date of the double-blind injection.
- Adverse Events that started on the Oral Lurasidone tablet period and continued the double-blind injection, but the severity did not change the AE will be reported in the Oral Lurasidone tablet period. If the severity of the AE gets worse, the AE will be considered in the double-blind injection period.

AEs will be summarized by treatment and by MedDRA system organ class (SOC) and Preferred Term (PT).

An overall summary of number of subjects within each of the categories described in the sub-section below, will be provided as specified in the SAP.

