## DOUBLE-BLIND INJECTION PERIOD

START DATE	STOP DATE	ACTION
Known	Known	If start date < injection start date and after oral tablet, then not AE If start date >= injection start date, then AE
	Partial	If start date < injection start date and after oral tablet, then not AE If start date >= injection start date and after oral tablet, then AE
	Missing	If start date < injection start date and after oral tablet, then not AE If start date >= injection start date and after oral tablet, then AE
Partial, could be on or after injection start date	Known	If stop date >= injection start date, then AE
	Partial	Impute stop date as latest possible date (i.e. last day of month if day unknown or 31st December if day and month are unknown), then: If stop date >= injection start date, then AE
	Missing	Assumed AE

Document:

Author:

Version Number:  
 Version Date:

Final Draft  
 11APR2019

Template No: CS\_TP\_BS016 Revision 4  
 Effective Date: 01Apr2016

Reference: CS\_WI\_BS005

START DATE	STOP DATE	ACTION
Missing	Known	If stop date $\geq$ injection start date, then AE
	Partial	Impute stop date as latest possible date (i.e. last day of month if day unknown or 31st December if day and month are unknown), then: If stop date $<$ injection start date, then not AE If stop date $\geq$ injection start date, then AE
	Missing	Assumed AE

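### SAP Appendix 2 has no oral-period AE rule for dated events in tablet-treated subjects who are never injected, and puts some partly dated events in neither period or in both

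*SAP*

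**What the plan says.** The SAP describes the oral and injection periods in three places.

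- **SAP 6.1.1** defines the oral safety population (OSAF) as everyone who gave consent and "received at least one dose of Lurasidone oral tablet". Whether an injection followed is irrelevant.
- **SAP 18.1** says an oral-period AE "is defined as an AE that started on or after the first dose of the oral lurasidone tablet". The injection date is not part of that definition. For an event carried over into the injection period, it adds: "but the severity did not change the AE will be reported in the Oral Lurasidone tablet period". If the event worsens, it moves to the injection period.
- **SAP Appendix 2, Algorithm for Adverse Events,** has one table per period.
  - In the oral table, a known start is handled by "If start date >= oral tablet start date and before injection start date, then AE".
  - The partial-start row is labelled "Partial, could be on or after oral tablet start date and before injection start date". That row and the missing-start row, with a known or imputed stop, use "If stop date >= oral tablet start date and before injection start date, then AE".
  - In the injection table, the only partial-start row is "Partial, could be on or after injection start date".
  - When the stop is missing and the start is partial or missing, both tables assume an AE.

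Uninjected subjects are part of the design. Only subjects who tolerate the tablets, meaning no moderate AE, can be randomized (SAP 4.1). Alternates not needed to fill a cohort are discharged (SAP 4.2). On numbers, SAP 4.4 says: "Approximately 70 subjects are planned overall to ensure that up to 40 subjects receive lurasidone" suspension or placebo.

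**The concern.** For a subject with no injection, there is no date for an event to precede. The subjects most exposed to this gap include those whose tablet-phase AE kept them from being randomized, so the oral column could miss the events that show intolerance.

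The oral column matters for these subjects. The overall AE summary (Table 14.3.1.1) and the table of AEs leading to discontinuation (14.3.2.2) are titled for the injectable safety population. The oral column of Tables 14.3.1.2 to 14.3.1.4 and 14.3.2.1 is therefore the only AE summary that can include uninjected subjects.

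A second, smaller concern is that the two tables do not fit together for incomplete dates. An event can fall between them, or be taken by both.

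**Working it through.** The plan gives no figure to reproduce. The check applies the Appendix 2 rules as written.

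**(a) Never-injected subject, dates on or after the first tablet.** An absent injection date is taken as failing the pre-injection test. This is an assumption. It is also what SAS, the planned software (SAP 7.7), would return if a missing date were compared directly, because missing sorts lowest.

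| Start | Stop | Date tested | Oral-period result |
|---|---|---|---|
| Known | Known, partial or missing | Start | No rule met (3 combinations) |
| Partial | Known or partial | Stop | No rule met (2) |
| Partial | Missing | None, but the row label needs an injection date | Unclear (1) |
| Missing | Known or partial | Stop | No rule met (2) |
| Missing | Missing | None | AE (1) |

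So 3 + 2 + 2 = 7 of the 9 combinations meet no oral-period rule, including every fully dated event. By the SAP 18.1 definition, the events with a known start all count.

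Subjects affected: about 70 planned minus up to 40 injected = 30, and 30/70 = 43%. This is a ceiling. The 30 include screen failures who never take a tablet, and the documents do not split them, so the range is 0 to about 30.

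**(b) Partial start that must precede the injection, stop on or after it.** Example: tablet 28 August, injection 4 September, start August with day unknown, stop 10 September.

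- Oral table: the stop is after the first tablet but not before 4 September, so no action applies.
- Injection table: the latest possible start is 31 August, before 4 September, so the partial-start row does not apply.
- Result: neither period. With a known start of 29 August and the same stop, the event is an oral-period AE. SAP 18.1 also puts it there if severity is unchanged.

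With the day unknown, this needs a month boundary between Day -7 and Day 1. SAP 7.1 has no Day 0, so that interval is 7 days. Over the four calendar years 2018 to 2021 (48 months), 7 tablet dates per month cross a boundary: 48 × 7 = 336 of 1,461 days = 23.0%.

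**(c) Counted in both periods.**

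- Start and stop both missing: AE in both tables, for any injected subject.
- Tablet 8 August, injection 15 August, start August with day unknown, stop missing: the start could fall on either side of the injection, so both partial-start rows apply and both assume an AE.

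Neither table gives one period priority. For medications, SAP 14 expressly allows counting in both periods. For AEs there is no such statement, and SAP 18.1 gives one period to a carried-over event.

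**The case against.** The strongest reply is that (a) is silence, not exclusion. No row declares a never-injected subject's post-tablet event not to be an AE. A programmer could treat the pre-injection test as met when there was no injection, and SAP 18.1 and OSAF both point that way. This stands as far as it goes: a reader might infer that the oral AE rate **is** biased downward, and the documents do not establish that, because the result depends on coding they do not specify. What remains is that Appendix 2 is the operative algorithm, includes rows for fully known dates, and conflicts with 18.1 on its face. The choice should be written down.

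A reader might also infer that events vanish from the report. They do not: Listings 16.2.7.1 to 16.2.7.3 use the oral safety population and would show them. Nor would editing Appendix 2 bring these subjects into Tables 14.3.1.1 or 14.3.2.2, which omit them by population.

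A third tempting reading is that every partial-start event lasting past the injection is misclassified. If its start month includes the injection date, it goes to the injection period only. That is a reasonable single-period convention, and the fix below keeps it.

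Finally, subjects are inpatient from Day -12 to Day 15 and AEs are recorded throughout, so partial or missing onset dates in the tablet phase should be few. That stands, and it makes (b) and (c) rare.

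**Conclusion.** The point holds as a conflict between SAP Appendix 2 on one side and SAP 18.1 and the OSAF definition on the other. It is minor and cheap to repair.

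- **(a) is the main part.** It involves 0 to about 30 of about 70 planned subjects and affects the oral column of four summary tables. It rests on a literal reading, or on code in which a missing date sorts lowest. It would be wrong to size it by a six-subject dose column: it concerns the oral column, where one subject among 40 to 70 is 1/40 = 2.5 down to 1/70 = 1.4 percentage points.
- **(b)** needs both a partial AE date and a month boundary between tablet and injection (about 23% of dates). The 23% is not a rate of misclassified events.
- **(c)** needs a missing stop together with a missing or ambiguous start.

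The documents give no frequency for incomplete AE dates, so (b) and (c) cannot be sized further.

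**What to change.** In the Appendix 2 AE tables:

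1. In the oral table, replace *and before injection start date* with *and (before injection start date or no injection given)*, including in the partial-start row label.
2. Keep the existing rule that a stop before the first tablet makes the event a pre-treatment event. Steps 3 and 4 apply only after it.
3. If the known parts of a partial start show that it precedes the injection, and it could be on or after the first tablet, class the event as oral even if it stops after the injection.
4. If the start could be on or after the injection and the stop does not rule that out, class the event as injection period only.
5. Assign events with both dates missing to one period: injection if the subject was injected, otherwise oral.
6. Reconcile the injection-table rule that a known pre-injection start is not an AE for that period with the SAP 18.1 rule that moves a worsening event into it.

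The cost is a few words in Appendix 2 and the matching derivation code, with no change to data collection. It should be settled before database lock, so that the choice is not made in programming afterwards.

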## DOUBLE-BLIND INJECTION PERIOD

START DATE	STOP DATE	ACTION
Known	Known	If start date < injection start date and after oral tablet, then not AE If start date >= injection start date, then AE
	Partial	If start date < injection start date and after oral tablet, then not AE If start date >= injection start date and after oral tablet, then AE
	Missing	If start date < injection start date and after oral tablet, then not AE If start date >= injection start date and after oral tablet, then AE
Partial, could be on or after injection start date	Known	If stop date >= injection start date, then AE
	Partial	Impute stop date as latest possible date (i.e. last day of month if day unknown or 31st December if day and month are unknown), then: If stop date >= injection start date, then AE
	Missing	Assumed AE

Document:

Author:

Version Number:  
 Version Date:

Final Draft  
 11APR2019

Template No: CS\_TP\_BS016 Revision 4  
 Effective Date: 01Apr2016

Reference: CS\_WI\_BS005

START DATE	STOP DATE	ACTION
Missing	Known	If stop date $\geq$ injection start date, then AE
	Partial	Impute stop date as latest possible date (i.e. last day of month if day unknown or 31st December if day and month are unknown), then: If stop date $<$ injection start date, then not AE If stop date $\geq$ injection start date, then AE
	Missing	Assumed AE

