Subjects will receive oral lurasidone 80 mg tablets on Day -7 and Day -6 (one dose per day), and be monitored for 5 days to ensure the subject is able to tolerate lurasidone (ie, absence of moderate adverse events). Subjects who tolerate dosing with oral lurasidone 80 mg will be eligible for randomization to receive a single lurasidone injectable suspension or placebo injection on Day 1.

For Cohort 1, a sentinel group of 2 subjects will be dosed in a 1:1 ratio (lurasidone injectable suspension: placebo injection). A 7-day clinical assessment of safety and tolerability (including AEs, vital signs, and other clinically relevant findings) for the sentinel subjects will be made by the Investigator (ie, Day 2 to Day 8). The remaining subjects will be randomized in a 5:1 ratio (lurasidone injectable suspension: placebo injection). A sentinel group may not be required for future dose cohorts: absence of an immune response will obviate the need for sentinel dosing after Cohort 1.

Subjects who are discharged after Day 15 will check into the clinical site again on Days 22 and 29 for scheduled assessments. Subjects will follow protocol procedures to remain in-clinic through Day 33 as they restart their prior medications (including antipsychotics), under observation of the Investigator/clinical site staff (ie, restabilization period).

Subjects who remained in-clinic through Day 29 will remain inpatient through Day 33 as they restart their prior medications (including antipsychotics) under observation of the Investigator/clinical site staff

Name of Investigational Product: Lurasidone injectable suspension

Name of Active Ingredient: Lurasidone (DSP-1349M)

(ie, restabilization period).

The restabilization period may be longer and subjects may remain in-clinic, as deemed necessary by the Investigator.

Subjects who discontinue the study prior to Day 29 will undergo assessments scheduled for Day 29 at the time of discontinuation (see Table 2). Subjects who discontinue the study after Day 29 but prior to Day 61 will undergo assessments scheduled for Day 61 at the time of discontinuation (see Table 2). Subjects who complete the study per protocol will return to the clinic for a follow-up safety assessment on Day 61 ± 2).

Dose Escalation/Safety Cohort Review

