11. SAFETY REPORTING

11.1. Definitions

11.1.1. Adverse Events

An AE is any untoward medical occurrence associated with the use of a drug in humans, whether or not considered drug related.

Untoward medical occurrences that occur between the time of signing the informed consent form (ICF) and drug administration are pre-treatment events. Those that occur after administration of study drug are considered AEs. Pre-treatment hospitalizations that occur in accordance with local clinical practice during the screening period (for wash-out from prior or concomitant medications) will not be considered as SAEs and do not need to be reported as such. Any untoward event that may occur during the hospitalization must be recorded as a pretreatment event. If hospitalization is prolonged by an untoward event, the event must be reported as an SAE.

An AE can, therefore, be any unfavorable and unintended sign (including an abnormal or clinically significant laboratory finding), symptom, or disease occurring after the administration of a medicinal (investigational) product, whether or not considered related to the medicinal (investigational) product. AEs may include the onset of new illness and the exacerbation of pre-existing conditions.

The Investigator should attempt to establish a diagnosis of the event based on signs, symptoms, and/or other clinical information. In such cases, the diagnosis should be documented as the AE and not the individual signs/symptoms.

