### **18.1.1. ALL AEs**

AE tables will be summarized by oral Lurasidone tablet period and double-blind injection period (dose level of Lurasidone injectable suspension and pooled placebo).

AE tables will be summarized by oral Lurasidone tablet period and double-blind injection period (dose level of Lurasidone injectable suspension and pooled placebo).

Injection site reaction related AEs summary tables and figure will be presented by ISAF population.

Listing of all AEs will also be presented by OSAF population..

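### The known-start rows of the SAP Appendix 2 injection-period AE algorithm omit the worsening exception in SAP 18.1, so the two rules place the same event in different periods

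*SAP*

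**What the plan says.** SAP 18.1 gives three rules for assigning AEs to periods. An oral-period AE starts on or after the first tablet. For the injection period, "Adverse Events for the double-blind Injection period is defined as an AE that started on or after the date of the double-blind injection". The third rule covers events that span both periods: if severity is unchanged, the event is reported in the oral period, but "If the severity of the AE gets worse, the AE will be considered in the double-blind injection period".

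SAP Appendix 2 turns period assignment into an algorithm. In its injection-period table, every row with a known start date (stop date known, partial or missing) contains "If start date < injection start date and after oral tablet, then not AE". The matching oral-period table says of the same event "If start date >= oral tablet start date and before injection start date, then AE". Neither table mentions severity.

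The tables are split along this line. SAP 18.1.1 says "AE tables will be summarized by oral Lurasidone tablet period and double-blind injection period", the latter by dose level and pooled placebo. Appendix 1 gives Oral Lurasidone 80 mg its own treatment group.

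**The concern.** Subjects may be randomized only if they tolerated oral lurasidone, which the Protocol synopsis explains as "absence of moderate adverse events". An AE carried into the injection period should therefore be mild. If it becomes moderate or severe after the depot injection, that is a post-injection safety observation, and the worsening rule in 18.1 exists to show it under the injected treatment.

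A programmer who follows Appendix 2 would leave that event under the oral tablet. The injection-period incidence and severity tables would then omit it. If the single record carries its worst severity, the oral column would show a severity reached only after injection. The sample size sections of both documents describe the primary endpoints as safety, and AE incidence is the first safety endpoint listed, so these tables matter.

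**Working it through.** No sample size or power figure is involved. The check applies both rules to one case and then sizes the effect of one misplaced subject.

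**1. Worked case (illustrative).** A mild AE starts on Day -6, becomes severe on Day 3 and stops on Day 10. Injection is on Day 1. The worsening is recorded on the original AE record.

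| Rule | Test applied | Result |
|---|---|---|
| SAP 18.1, third rule | Began in the oral period, continued past injection, severity worsened | Injection-period AE |
| Appendix 2, injection period, known start | Day -6 is before Day 1 and after the first tablet (Day -7) | Not an injection-period AE |
| Appendix 2, oral period, known start | Day -6 is on or after Day -7 and before Day 1 | Oral-period AE |

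The stop date makes no difference, because the three known-start rows use the same condition.

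**2. Which events are affected.** Only those with a known start date before injection. For a start date classed as "Partial, could be on or after injection start date", or a missing one, Appendix 2 decides by the stop date: a stop on or after injection makes it an injection-period AE, and a missing stop date is assumed to do so. A poorly dated event can therefore enter the injection period while a fully dated one with documented worsening cannot.

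**3. Whether such records can exist.** SAP 18.1.1.1 has a severity rule for AEs that start after the first tablet and end during the injection period, so it contemplates single records spanning both periods. Protocol 11.3 has each AE evaluated for severity and duration and gives no instruction to split a record when severity changes.

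**4. Effect of one subject.** Inputs: 6 active and 2 placebo subjects per cohort and up to 5 cohorts (Protocol 14.1 and synopsis; SAP 4.1 and 4.4).

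- Dose group: 1/6 = 16.7, about 17 percentage points.
- Pooled placebo if all five cohorts run: 5 × 2 = 10 subjects, so 1/10 = 10 percentage points.

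These are upper limits for a given row. Protocol 14.3.5.1 counts each subject once per system organ class and preferred term, so a row moves only if the subject has no other qualifying injection-period event in it.

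**The case against.** The strongest reply is that 18.1 is the substantive definition and already contains the right rule, while Appendix 2 is titled as a set of partial-date conventions. On that view its known-date rows merely restate the second rule of 18.1, and a careful programmer would apply the third as well. This has some force. But the AE part of Appendix 2 is headed as an algorithm and begins with rows in which both dates are known. It can be programmed as the complete rule, and nothing gives 18.1 precedence.

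The second reply is that sites may open a new record when an AE worsens. The start date would then fall after injection and the two rules would agree. Protocol 11.1.1 gives some support: "AEs may include the onset of new illness and the exacerbation of pre-existing conditions". Protocol 10.2.3 also has worsened physical examination findings recorded as AEs after dosing. Neither settles the practice for AEs in general, and the CRF completion instructions are not among the documents. The point is therefore conditional on worsening being held on the original record.

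Third, a reader might infer that these events disappear, or that dose escalation is compromised. The documents do not support either. The event stays in the oral-period tables and in the AE listing. Dose decisions rest on the Safety Review Team's review, and Protocol 9.3 itself excludes AEs that start before injection from the stopping criteria. SAP 18 plans no statistical comparison of treatment groups for safety data unless a section specifies one, so what is at stake is a descriptive tabulation.

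**Conclusion.** Wrong as written: SAP 18.1 and the known-start rows of Appendix 2 contradict each other on an oral-period AE that worsens after injection. Appendix 2 agrees with the second rule of 18.1 but leaves out the exception in the third. The contradiction in the text depends on no assumption. Its effect on the tables depends on worsening being held on the original record and on Appendix 2 being programmed as it stands.

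Under those conditions the event is misplaced, not removed. One subject shifts a row by up to 17 points in a dose group of 6, or 10 points in pooled placebo of 10. A reader might go further and estimate how likely it is that at least one such event is misplaced. The documents give no rate for worsening, so that probability cannot be calculated from them. Affected events must also have passed the oral tolerability check, persisted to injection and then worsened, which limits their number.

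**What to change.** In the three known-start rows of the Appendix 2 injection-period AE algorithm, add after the pre-injection condition: *unless severity worsened on or after injection, in which case AE in the injection period at the worsened severity (see 18.1)*.

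State one way of identifying worsening: either a dated severity change on the original record or a new AE record dated at the change. Using both without a rule against duplicates could count one worsening twice, and Protocol 14.3.5.1 plans event counts as well as subject incidence. If the original record is used, also say whether the oral-period table keeps the event at its pre-injection severity, because the oral-period rows would still claim it.

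The cost is a few words in a SAP still marked as a final draft and, if worsening is to be identified from a particular kind of record, a short CRF completion note. No design change or additional assessment is needed.
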